## 7. STUDY ASSESSMENTS AND PROCEDURES

Protocol waivers or exemptions are not allowed with the exception of immediate safety concerns. Therefore, adherence to the study design requirements, including those specified in the Time and Events Table, are essential and required for study conduct.

This section lists the procedures and parameters of each planned study assessment. The exact timing of each assessment is listed in the Time and Events Table (Section 7.1).

The following points must be noted:

- If assessments are scheduled for the same nominal time, THEN the assessments should occur in the following order:
  1. 12-lead ECG
  2. vital signs
  3. blood draws

Note: The timing of the assessments should allow the blood draw to occur at the exact nominal time.

- The timing and number of planned study assessments, including safety, pharmacokinetic, pharmacodynamic/biomarker assessments may be altered during the course of the study based on newly available data (e.g., to obtain data closer to the time of peak plasma concentrations) to ensure appropriate monitoring.
- The IRB/IEC will be informed of any safety issues that require alteration of the safety monitoring scheme or amendment of the Informed Consent Form.

Please refer to [Appendix 10](#) in Section 11.10 for study management information during the COVID-19 pandemic.

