- k. Women of childbearing potential only. SR=serum, UR=urine. Pregnancy events will be captured starting at Day 1 following initial exposure to study drug. Urine pregnancy test performed at Day 1 prior to administration of study drug, at Week 4b, and at study visits when other blood draws are not required in order to limit needle sticks. Serum pregnancy test can substitute for urine pregnancy test if locally required but must be appropriately timed to confirm pregnancy status prior to randomization and first IM administration. Pregnant participants who remain in the study do not need pregnancy testing during the study, for the duration of their pregnancy. Pregnant participants remaining in the study have additional assessments required, as described in [Appendix 11](#).
- l. Week 48, Week 96, and Week 152 HIV-1 RNA retest (within 4 weeks) for results  $> 50$  c/mL will be captured as unscheduled visit. Plasma for storage samples will be used for possible future analyses.
- m. A morning specimen is preferred. To assess biomarkers: urine albumin/creatinine ratio; urine protein/creatinine ratio; and urine phosphate. Urine phosphate results from visit 4a are not required by protocol to inform the safety review at visit 4b prior to receipt of initial CAB LA + RPV LA injections.
- n. An overnight fast is preferred; however, a minimum of a 6-hour fast is acceptable.
- o. Only collect if the Withdrawal visit occurs at Week 48, Week 96, or Week 152.
- p. Whole blood/PBMC collection samples may be used for virologic analyses. PBMCs will be collected at baseline Day 1, Week 48, Week 96, Week 152 or Withdrawal if prior to Week 152.
- q. Genetics sample should be collected only for patients who did not participate in the 201585(ATLAS) study (sample was previously collected and stored). Informed consent for genetic research must be obtained before sample collection. Sample may be collected at any visit after signing informed consent, but preferably at the Day 1 visit.

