Pregnancy Testing k	S	U	S	U	S		S	S	S	S		S	S	S	S	S	S	S	S	S	S	S	S	S
HIV-1 RNA and sample for storage (S) l	X	X		X	X		X	X	X	X		X	X	X	X	X	X	X	S	X	X	X	X	X
CD4+ cell count	X	X		X	X		X	X	X	X		X	X	X	X	X	X	X	X	X	X	X	X	X
CD8+ cell count		X						X				X									X	X		
Urinalysis m		X	X					X				X									X	X		
Fasting Labs Glucose, Cholesterol (Total, HDL and LDL) and Triglycerides n		X										X									X	X o		

Procedure	Screening Visit a	Maintenance Phase																		Extension Phase		Withdrawal Assessments y (Maintenance)	WD assessments (Extension)	Long-Term Follow-up z
		Day 1	Week																	Q8W After Week 96	152			
			Week 4A (Oral lead-in ONLY) b	Week 4B (Oral lead-in ONLY) b	8	9	16	24	32	40	41	48	56	64	72	80	88	96	100					
IM treatment administration when transitioning from CAB + RPV Q4W	X			X		X	X	X	X		X	X	X	X	X	X	X		X	X				
Patient Reported Outcomes u																								
HAT-QoL (short-form)	X						X				X											X		
HIV TSQs	X						X				X									X		X		
HIV TSQc v											X											X		
ACCEPT	X							X			X									X		X		
Reason for Switch or Reason for continuation w	X																							
Preference Questionnaires x											X										X		X	
PIN					X			X			X										X		X	
Safety Follow Up Visit (for subjects completing the study, may or may not be transitioning to CAB + RPV LA marketed product) and Safety Follow Up Visit (for subjects withdrawing from the study) are required as described in Section 5.6.																								

bb. Complete all Screening assessments within 35 days. Participants may begin the Maintenance Phase as soon as all Screening assessments are complete. Participants may be rescreened once and will be assigned a new participant number. Participants transitioning from the 201585 (ATLAS) study must reach ATLAS Week 48 (at minimum) prior to initiating Screening procedures for ATLAS-2M and must reach ATLAS Week 52 (at minimum) prior to randomization in ATLAS-2M.

- cc. Visits Weeks 4A and 4B are part of the CAB + RPV Oral Lead-in period and are required only for participants transitioning from current SOC to CAB LA + RPV LA.
- dd. Confirmation of eligibility to continue the Maintenance Phase, and eligibility to enter the Extension Phase.

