- ee. Collect full routine medical history plus (report at Baseline visit): HIV risk factors (may be collected at a later study visit), cardiovascular risk factors (assessments include smoking status and history, family history of cardiac events), recent [ $\leq 6$  months] illicit drug use, intravenous drug use, gastrointestinal disease, metabolic, psychiatric, renal, bone, and neurologic disorders.
- ff. Physical exams should be conducted as part of normal routine clinical care. Medical assessments include any decisions the study staff must make for participants management and/or care of participant.
- gg. Height collected at Baseline Day 1 only.
- hh. Measure vital signs after about 5 minutes of rest in a semi-supine position.
- ii. A 12-lead ECG will be performed after resting in a semi-supine position for at least 5 minutes. ECGs will be performed pre-dose. For participants transitioning from ATLAS, the pre-dose Week 48 ECG can also serve as the ATLAS-2M Screening ECG. ECG pre-dose will be performed in triplicate at Day 1. A 2-hour post-dose ECG will also be performed at Days 1 and Week 48 for participants receiving CAB LA + RPV LA with an allowable window of  $\pm 30$  minutes.
- jj. Only SAEs related to study participation or to a concomitantly administered ViiV/GSK product will be collected between obtaining informed consent and administration of study drug at Day 1.
- kk. On Day 1, the eC-SSRS is to be administered prior to randomization. The eC-SSRS will preferably be completed at the beginning of the visit following administration of other PROs required prior to injections. The eC-SSRS is not required during the Withdrawal visit if withdrawal occurs during the Extension Phase.
- ll. Women of childbearing potential only. SR=serum, UR=urine. Pregnancy events will be captured starting at Day 1 following initial exposure to study drug. Serum pregnancy test can substitute for urine pregnancy test if locally required but must be appropriately timed to confirm pregnancy status prior to randomization and first IM administration. Pregnant participants who remain in the study do not need pregnancy testing during the study, for the duration of their pregnancy. Pregnant participants remaining in the study have additional assessments required, as described in [Appendix 11](#).

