## 7.4. Safety

### 7.4.1. Clinical Evaluations

The following clinical evaluations will be performed according to the Time and Events schedule:

- Monitoring and recording of all AEs and SAEs. Additional information on the Time Period and Frequency of Detecting AEs and SAEs is provided in Section 7.4.3.1.
- Physical exams should be conducted as part of normal routine clinical care. Abnormalities noted during any exam must be recorded in the eCRF (e.g., in the current medical conditions or AE logs).
- Height and weight will be measured and recorded. Height collected on the Day 1 (Baseline) only.
- Vital signs will include systolic and diastolic blood pressure and heart rate collected after resting for about 5 minutes. Temperature will also be collected.
- Past medical history, family history, social history, medication history. Targeted history on cardiovascular risk (smoking history, family and personal history).
- HIV-associated conditions will be recorded.
- Electrocardiogram: A 12-lead ECG will be performed in a semi-supine position after 5 minutes of rest. On Day 1 (Baseline) of the Maintenance Phase, ECGs should be performed in triplicate prior to first dose. An ECG machine that automatically calculates the heart rate and measures PR, QRS, QT, and QTc intervals is preferred, and these calculated numbers can be used for reporting purposes. Otherwise, an appropriately qualified ECG reader must interpret the results. The same interpreter should assess all ECGs for each participant for the site. Regardless, each ECG should be reviewed by a qualified ECG reader. The qualified ECG reader will make the non-calculated ECG interpretations. The same QT correction formula must be used for each individual participant to determine eligibility for and discontinuation from the study. This formula may not be changed or substituted once the participant has been enrolled.
- Regular monitoring of hematology, blood chemistry, urinalysis and fasting glucose and lipids (parameters to be tested listed below).
- Periodic assessment of glucose, insulin, and bone, cardiovascular, and renal markers;
- Pregnancy testing. A negative urine pregnancy test is required prior to initiation of IP, any dose of CAB LA or RPV LA or as required by the Medical Monitor following a treatment interruption(s). If serum testing is required locally, the results should be available prior to the visit where urine testing is indicated per the Time and Events Schedule (Section 7.1).

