#### **7.4.2. Laboratory Assessments**

All protocol required laboratory assessments, as defined in the Time and Events Schedule (see Section [7.1](#)), must be performed by the central laboratory. Laboratory assessments must be conducted in accordance with the Central Laboratory Manual and Protocol Time and Events Schedule. Laboratory requisition forms must be completed and samples must be clearly labeled with the participant number, protocol number, site/centre number, and visit date. Details for the preparation and shipment of samples will be provided by the central laboratory. Reference ranges for all safety parameters will be provided to the site by the central laboratory.

- The investigator must review the laboratory report, document this review, and record any clinically relevant changes occurring during the study in the AE section of the CRF. The laboratory reports must be filed with the source documents. Clinically significant abnormal laboratory findings are those which are not associated with the underlying disease, unless judged by the investigator to be more severe than expected for the participant's condition.
- All laboratory tests with values considered clinically significantly abnormal during participation in the study should be repeated until the values return to normal or baseline or are no longer considered significantly abnormal by the investigator or medical monitor.

- If such values do not return to normal/baseline within a period of time judged reasonable by the investigator, the etiology should be identified and the sponsor notified.
- All protocol-required laboratory assessments, must be conducted in accordance with the laboratory manual and the protocol Time and Events table.

If additional non-protocol specified laboratory assessments are performed at the institution's local laboratory and result in a change in subject management or are considered clinically significant by the investigator (e.g., SAE or AE or dose modification) the results must be recorded in the eCRF. Local laboratory services may be used to verify pending laboratory parameters only after consultation and agreement with the study team.

Refer to the lab manual for appropriate processing and handling of samples to avoid duplicate and/or additional blood draws.

Labs will be automatically graded by the central lab according to the DAIDS toxicity scales (See Section 11.2 "Division of AIDS Table for Grading the Severity of Adult and Pediatric Adverse Events").

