- CD8+ cells will only be reported at Baseline, Day 1, Weeks 4b, 24, 48, 96 and 152.
- HBV DNA will only be performed for participants with a positive anti-HBc and negative HBsAg and negative anti-HBs (past and/or current evidence).
- Urine pregnancy test/ serum pregnancy test will be performed according to the Time and Events Table (Section 7.1).

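### Section 7.4.1 requires a negative urine pregnancy test before any long-acting dose, but the Q8W schedule has serum only at Week 8 and every later injection visit

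*Protocol*

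**What the plan says.** Section 7.4.1 gives the rule: "A negative urine pregnancy test is required prior to initiation of IP, any dose of CAB LA or RPV LA". Its opening line ties the list to the visit schedule: "The following clinical evaluations will be performed according to the Time and Events schedule". Section 7 does the same for all assessments ("The exact timing of each assessment is listed in the Time and Events Table"), and the note to Table 8 does so for the type of test: "Urine pregnancy test/ serum pregnancy test will be performed according to the Time and Events Table".

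The Q8W table in Section 7.1.2 has one pregnancy-test row. It shows urine at Day 1 and Week 4B, and serum at Screening, Week 4A, Week 8 and every later visit except Weeks 9 and 41, which are blank.

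The footnotes (k in the Q4W table, ll in the Q8W table) let serum replace urine only where local rules demand it, and then the serum test "must be appropriately timed to confirm pregnancy status prior to randomization and first IM administration". In the Q4W table, footnote k places urine tests at Day 1, then "at Week 4b, and at study visits when other blood draws are not required in order to limit needle sticks". Section 7.4.2 says that protocol-required laboratory tests "must be performed by the central laboratory".

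**The concern.** The text makes a negative urine result a condition of each long-acting dose. The schedule that sites are told to follow provides no urine test at almost all Q8W injections. A serum sample drawn on the day of injection meets the condition only if the result is back before dosing, and for later injections nothing shown requires that.

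The stake is a specific safeguard. Section 7.4.1 also bars further study drug in a pregnant participant until benefit and risk have been discussed with her and a pregnancy consent addendum is signed. That protection works only once the pregnancy is known, and a long-acting injection cannot be taken back. Drug from earlier injections would be present anyway, so the issue is one further dose given without the discussion, not first exposure.

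**Working it through.** No sample size, power or error-rate figure is involved. The check is an alignment of the table with the text, followed by a count.

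**Step 1: read the Q8W pregnancy row.** The header has 24 columns: Screening, Day 1, 4A, 4B, 8, 9, 16, 24, 32, 40, 41, 48, 56, 64, 72, 80, 88, 96, 100, Q8W after Week 96, 152, two withdrawal columns and long-term follow-up. The row reads S, U, S, U, S, blank, S, S, S, S, blank, then thirteen S: 5 + 1 + 4 + 1 + 13 = 24 cells. Row and header match, so the reading is unambiguous. The two blanks (Weeks 9 and 41) are pharmacokinetic visits without an injection.

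**Step 2: list the injections.** Sections 6.9.1.2 and 6.9.1.4 give them:

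- Entrants from oral standard of care: 4b, 8, 16, 24, 32, 40, 48, then every 8 weeks.
- Entrants from ATLAS Q4W: Day 1, 8, 16, 24, 32, 40, 48, then every 8 weeks.

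In both groups only the first injection falls on a urine visit.

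| Period | Injections | Serum only | Share |
|---|---|---|---|
| Through Week 48 | 7 | 6 | 6/7 = 86% |
| Through Week 96 (adds 56, 64, 72, 80, 88, 96) | 13 | 12 | 12/13 = 92% |
| Through Week 152 (adds 104, 112, 120, 128, 136, 144, 152) | 20 | 19 | 19/20 = 95% |

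**Step 3: look for a rule that bridges the gap.**

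- The substitution of serum for urine applies only where locally required, whereas the table sets serum for every site.
- Section 7.4.1 asks that locally required serum results be ready before visits at which the table indicates urine. After Week 4B the Q8W table indicates none.
- The footnotes fix timing for randomization and the first injection only.
- Before the first injection the schedule does provide lead time. Serum falls at an earlier visit (Screening or Week 4A) and urine on the dosing day. For entrants from standard of care, Section 1.4.2.1.2 lets the Week 4b injection go ahead once the Week 4a central results are in, and Section 6.9.1 allows up to 2 weeks between the visits where possible. Nothing comparable is shown for later injections.

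**Step 4: scale.** With 1020 participants randomized 1:1 and the 25% enrolment goal for women (Section 4.3), the Q8W arm would hold 1020 / 2 × 0.25 = 127.5, about 128 women. How many are of childbearing potential is not given.

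**Q4W table.** Footnote k implies the same pattern at visits with other blood draws, and the row appears to show serum alone at Weeks 8, 16, 24, 32 and 40. That row extracts imperfectly, so this is provisional and no ratio is given.

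**The case against.** The strongest reply is that both texts can be obeyed. The table lists scheduled tests, Section 7.4.1 adds a condition for dosing, and a site that injects on a pending serum result breaches an explicit sentence. That is true of a careful site. But the same section, Section 7 and Table 8 all send sites to the table for timing and test type, so a site working from the schedule has no prompt for the urine test.

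A second reply is that the rule was meant for the first injection only, since the footnotes name that point. The footnotes, however, say first where they mean first; Section 7.4.1 says any dose and lists it separately from initiation of study drug. Serum at blood-draw visits is deliberate, to limit needle sticks, but that reason does not bear on a urine test.

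Several limits stand:

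- Section 7.4.7.1, on pregnancy testing, was not available and may settle the matter.
- Serum turnaround is not stated. The gap between Weeks 4a and 4b serves a general safety-laboratory review and only suggests that results take longer than a day.
- The central-laboratory sentence, read literally, would also cover urine tests, yet Section 7.2.2 needs the Day 1 urine result before randomization. It does not establish where, or how fast, later tests are run.
- Highly effective contraception is mandatory, every Q8W injection visit has some pregnancy test, and pregnant participants may stay on treatment after discussion and consent.

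These points limit the harm. They do not reconcile the text with the table.

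**Conclusion.** The concern holds. As written, the Q8W schedule does not deliver the test that Section 7.4.1 requires at any injection after the first: 6 of 7 through Week 48, 12 of 13 through Week 96, and 19 of 20 through Week 152 for those who continue. These counts are scheduled injections without a urine test, not untested injections or missed pregnancies. That a dose might be given before status is known rests on the assumption that serum results are not back the same day. The conclusion is also subject to Section 7.4.7.1. The gain from correcting it is modest and concerns participant safety; endpoints, power and analysis are not touched. Confidence is medium.

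**What to change.** For women of childbearing potential not known to be pregnant:

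1. Add a pre-dose point-of-care urine test to the Time and Events tables at injection visits that now have serum only.
2. Amend footnotes k and ll to require a negative result, either urine or a serum result already available, before every injection.
3. Reword the sentence in Section 7.4.1 to match, and check all three changes against Section 7.4.7.1.

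The cost is some table entries, two footnotes and one sentence, plus one urine test per serum-only injection visit. For the Q8W arm through Week 96 the upper bound is 127.5 × 12 = 1,530 tests, which assumes that every woman is of childbearing potential and stays on treatment. No visit or blood draw is added.

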#### **7.4.2. Laboratory Assessments**

All protocol required laboratory assessments, as defined in the Time and Events Schedule (see Section [7.1](#)), must be performed by the central laboratory. Laboratory assessments must be conducted in accordance with the Central Laboratory Manual and Protocol Time and Events Schedule. Laboratory requisition forms must be completed and samples must be clearly labeled with the participant number, protocol number, site/centre number, and visit date. Details for the preparation and shipment of samples will be provided by the central laboratory. Reference ranges for all safety parameters will be provided to the site by the central laboratory.

- The investigator must review the laboratory report, document this review, and record any clinically relevant changes occurring during the study in the AE section of the CRF. The laboratory reports must be filed with the source documents. Clinically significant abnormal laboratory findings are those which are not associated with the underlying disease, unless judged by the investigator to be more severe than expected for the participant's condition.
- All laboratory tests with values considered clinically significantly abnormal during participation in the study should be repeated until the values return to normal or baseline or are no longer considered significantly abnormal by the investigator or medical monitor.

- If such values do not return to normal/baseline within a period of time judged reasonable by the investigator, the etiology should be identified and the sponsor notified.
- All protocol-required laboratory assessments, must be conducted in accordance with the laboratory manual and the protocol Time and Events table.

If additional non-protocol specified laboratory assessments are performed at the institution's local laboratory and result in a change in subject management or are considered clinically significant by the investigator (e.g., SAE or AE or dose modification) the results must be recorded in the eCRF. Local laboratory services may be used to verify pending laboratory parameters only after consultation and agreement with the study team.

Refer to the lab manual for appropriate processing and handling of samples to avoid duplicate and/or additional blood draws.

Labs will be automatically graded by the central lab according to the DAIDS toxicity scales (See Section 11.2 "Division of AIDS Table for Grading the Severity of Adult and Pediatric Adverse Events").

For fasting laboratory assessments, an overnight fast is preferred; however, a minimum of a 6 hour fast is acceptable.

Table 8 includes lab parameters to be assessed as per the Time and Events Schedule (see Section 7.1). In addition to the protocol-specified laboratory assessments the study Medical Monitor, in collaboration with the site investigator, may request additional central laboratory assessments be performed to support safety profiling and case management of individual study participants.

